| Definitions: | 
CAPTURE+ = Participants with
 
• CAPTURE score ≥ 5, or• CAPTURE score of 2, 3, or 4 with a low PEF, defined as <350 L/min for males and <250 L/min for females 
CAPTURE- = Participants with CAPTURE score < 2 or scores 2-4 with normal PEF, defined as ≥ 350 L/min for males and ≥ 250 L/min for females
 
Spirometrically defined COPD = Participants with abnormal spirometry, defined as post-bronchodilator $FEV_1/FVC < 0.7$. If a participant is unable to complete a post-bronchodilator spirometry (refusal, technical error on the part of coordinator, etc.), and the pre-bronchodilator FEV_1/FVC is less than 0.65, the participant will be considered to have COPD for the purpose of follow-up in this study.
 
Clinically significant COPD = Participants with abnormal spirometry, defined as post-bronchodilator $FEV_1/FVC < 0.7$, plus one of the following:
 
• $FEV_1 < 60\%$ predicted, or• ≥ 1 exacerbation-like event within the past 12 months. 
Mild COPD = Participants with abnormal spirometry, defined as post-bronchodilator $FEV_1/FVC < 0.7$ plus both of the following:
 
• $FEV_1 \geq 60\%$ and• No prior history of ECOPD 
Preserved ratio, impaired spirometry (PRISm) = Participants without spirometrically defined COPD who have post-bronchodilator $FEV_1 < 80\%$ predicted.
 
Symptomatic non-obstructed (SNO) = Participants without spirometrically defined COPD and without PRISm who have a COPD Assessment Test score ≥ 10.
 |

| | |
|--------------------|--|
| Objectives: | Aims 1 and 3 Primary Objectives: 
• Aim 1 - Define the sensitivity and specificity of CAPTURE for identifying previously undiagnosed patients with clinically significant COPD in a broad range of primary care settings. |
| | 
• Aim 3 – Define the impact of CAPTURE information provided to clinicians in identifying and managing CAPTURE+ patients across a broad range of primary care settings. 
Aim 2 Primary Objective: Explore clinical practice implementation approaches to and acceptance of CAPTURE case finding for clinically significant COPD in a range of primary care practices.
 |

| | |
|--|--|

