A comprehensive, qualitative study identified key constructs for identifying recently diagnosed patients with clinically significant COPD. We completed a two phase study that included focus groups followed by cognitive interviews to refine the key constructs for identifying patients with clinically significant COPD.(43) Fifty participants were recruited including those with mild airflow obstruction, diagnosed within the previous six months and without previous ECOPD; those diagnosed within the previous six months and with a history of at least one ECOPD within the prior year; those with 2-3 risk factors for COPD but without CAO; and those with ≥ 4 risk factors for COPD but without CAO. Using a content analysis approach, key themes and constructs were identified and integrated with the content of the previous literature review and data mining. We identified 44 candidate items that resonated with patients and provided important insights into a case finding instrument.

A five-item questionnaire exhibits excellent operating characteristics to identify clinically significant COPD patients. We completed a prospective, multi-site, case-control study of four groups: cases with clinically significant COPD – COPD with ≥ 1 ECOPD in the previous year (n=97) and COPD with no ECOPD but an $FEV_1 < 60\%$ predicted (n=89); controls – no known COPD (n=87) and COPD with an $FEV_1 > 60\%$ predicted and no ECOPD in the previous year (n=74). Using random forest analyses the 44 candidate items were reduced to 34-item, 21-item, 8-item and two different five-item sets. Through-out the item reduction process, the item sets maintained good performance, consistently misclassifying fewer than 27% of cases and controls, and with sensitivity greater than 80% and specificity greater than 70%. A five-item questionnaire exhibited good operating characteristics for separating COPD cases from controls. These characteristics were even better when separating COPD from controls without COPD.

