Demographic data including date of birth, gender, ethnicity, race, educational level achieved, daily work schedule, living arrangement and health insurance will be entered into the EDC system.

Contact information including address, phone numbers and email address will be obtained. Alternate contact information will be obtained for two other people, family members not living with the participant or close contacts, who may be knowledgeable about the participant in the event that the participant cannot be contacted for subsequent longitudinal follow-up. Alternate contact information will include name, address, phone numbers and email addresses. All contact information will be stored securely at the clinical site or in a database separate from that developed for the clinical data.

Medical History

Previous medical diagnoses will include comorbidities such as cardiovascular, respiratory and malignant disorders. Influenza vaccination history will also be recorded. This questionnaire will be completed under supervision of the coordinator.

Concomitant Medication Review

Respiratory medications will be recorded at baseline for all participants. This questionnaire will be completed under supervision of the coordinator.

CAPTURE Additional Items Questionnaire

Participants will complete the 13-item *self-administered* questionnaire.

COPD Assessment Test (CAT)

Participants will complete the 8-item *self-administered* questionnaire.

Respiratory symptoms, smoke exposure and exacerbation like events

History of respiratory symptoms and exacerbation like events over the past year as well as smoke exposure (including e-cigarette or equivalent) will be recorded. This questionnaire will be completed

Whenever possible, informed consent, eligibility review, CAPTURE Questionnaire and PEF will be performed prior to the participant's clinic appointment, so that CAPTURE results may be provided to the physician at the time of his/her appointment if the patient is cared for in a clinical center randomized to CAPTURE+ education.

COVID-19 Additional Items Questionnaire

Participants will complete the 18-item *self-administered* questionnaire.

Adverse events

Adverse events related to study procedures will be recorded by the coordinator.

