Patients who are eligible and agree to participate in the study sign informed consent, complete the CAPTURE questionnaire, PEF testing, spirometry testing, other respiratory questionnaires, provide past medical history, and demographic information. Local/PBRN study coordinators perform the study procedures and record baseline information into the electronic data capture (EDC) system. The study coordinators calculate a CAPTURE score for each participant. For patients in a practice randomized to CAPTURE+COPD education, their practitioner is provided with CAPTURE results for their patient. Practitioners at sites randomized to the COPD education only intervention are blinded to CAPTURE scores. Practitioners in both intervention arms are blinded to research spirometry results.

Based on the data collected at baseline, participants will be classified into the following groups for analyses:

| Cohort | Definition |
|------------------------------|---|
| CAPTURE+ | Participants with 
 • CAPTURE score ≥ 5, or • CAPTURE score of 2, 3, or 4 with a low PEF, defined as <350 L/min for males and <250 L/min for females |
| CAPTURE- | Participants with 
 • CAPTURE score < 2 or scores 2-4 with normal PEF (defined as ≥ 350 L/min for males and ≥ 250 L/min for females) |
| Spirometrically Defined COPD | Participants with abnormal spirometry, defined as post-bronchodilator $FEV_1/FVC <0.7$. If a participant is unable to complete a post-bronchodilator spirometry |

| | |
|--|---|
| | (refusal, technical error on the part of coordinator, etc.), and the pre-bronchodilator FEV_1/FVC is less than 0.65, the participant will be considered to have COPD for the purpose of follow-up in this study. |
| Clinically Significant COPD | Participants with abnormal spirometry, defined as spirometrically defined COPD plus at least one of the following: 
 • $FEV_1 < 60\%$ predicted or • ≥ 1 exacerbation like event within the past 12 months. |
| Mild COPD | Participants with spirometrically defined COPD plus both of the following: 
 • $FEV_1 \geq 60\%$ and • No prior history of ECOPD |

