| Preserved ratio, impaired spirometry (PRISm) | Participants without spirometrically defined COPD who have post-bronchodilator $FEV_1 < 80\%$ predicted. Among participants who do not complete post-bronchodilator spirometry and have pre-bronchodilator $FEV_1/FVC \geq 0.7$, those with $FEV_1 \geq 80\%$ predicted will be considered not to have PRISm and those with $FEV_1 < 80\%$ predicted will be considered to have undetermined PRISm status in primary analyses. |
| Symptomatic non-obstructed (SNO) | Participants without spirometrically defined COPD and without PRISm who have a COPD Assessment Test score ≥ 10 . |

Longitudinal Follow-up

A pre-defined subgroup of enrolled participants, who meet any of the below criteria, will undergo longitudinal follow-up at 12 months:

1. CAPTURE+ participants, as defined above.
2. Participants who have spirometrically defined COPD, as defined above, or post-bronchodilator $FEV_1 < 80\%$ predicted at baseline. If post-bronchodilator spirometry is not completed, then pre-bronchodilator $FEV_1 < 70\%$ predicted will be considered to satisfy this criterion for follow-up.
3. A random sample of approximately 5% who do not meet criteria 1 – 2.

Participants who meet the criteria for follow-up will be sent notification/reminder letters within the first three weeks of enrollment and at three, six, and nine months. Patient-reported data will be collected by COPD Foundation via telephone, secure web-based server, or mail-based methodologies, based on participant preference.

Subject medical data will be collected from the medical record to assess for changes in practice-level care.

[figure not shown]

Figure 1

The hypothesis for Aim 3 is that sites where COPD and CAPTURE education and patient-level CAPTURE data are provided to clinicians will exhibit improved COPD diagnosis and COPD-related care compared to sites where COPD education is provided to clinicians.

7 Inclusion-Exclusion Criteria and General Study Population for Aim 3

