Height and Weight: Height and weight will be recorded in order to determine appropriate prediction equations for spirometry and possible effect of obesity on spirometry. Height will be recorded in inches, and weight will be measured in pounds.

Demographic Data Collection: Demographic data including date of birth, gender, ethnicity, race, educational level, current employment status, living arrangement and health insurance will be entered into the EDC system.

Medical History: Previous medical diagnoses will include comorbidities such as cardiovascular, respiratory, and malignant disorders. Influenza vaccination history will also be recorded.

Statistical Analysis Plan

CAPTURE

Concomitant Medication Review: Respiratory medications will be recorded at baseline for all participants.

CAPTURE Additional Items Questionnaire: Participants will complete the 13 item self-administered questionnaire.

COPD Assessment Test (CAT): Participants will complete the eight item self-administered questionnaire. Each item is on a scale of 0-5 with higher scores indicating worse health status.

Respiratory Symptoms, Smoke Exposure and Exacerbation-Like Events: History of respiratory symptoms and exacerbation like events over the past year as well as smoke exposure (including e-cigarette or equivalent) will be recorded.

Adverse Events: Adverse events related to study procedures will be recorded by the coordinator.

Practice Characteristics: The locations of participating clinical practices will be categorized based on designation as rural by the Federal Office of Rural Health Policy (FORHP) / Health Resources & Services Administration (HRSA). A practice location will be classified as rural if the ZIP code appears in the Eligible ZIP Codes file downloadable from the FORHP website: <https://www.hrsa.gov/rural-health/about-us/definition/datafiles.html>. Other data describing the characteristics of participating practices will be collected from study site personnel.

6.6.2: Longitudinal follow-up

Follow-up efficacy assessments are collected from the time of baseline to 12 months in selected cohorts (as described in section 6.1).

Table 3: Data collected from medical records include:

| All participants undergoing 12-month follow-up as described in section 6.1 | Current Smokers Only |
|--|--|
| Clinical spirometry ordered or administered | Smoking cessation counseling |
| New recorded clinical diagnosis of COPD | New prescription for smoking cessation medication |

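### The secondary cohort definitions mislabel participants with a pre-bronchodilator ratio of 0.65 to <0.70 and no post test, differ between Protocol and SAP, and use unmatched exacerbation windows

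*SAP*

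**What the plan says.** SAP 6.1 sorts participants into cohorts from baseline data.

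- **Spirometric COPD** (both documents): post-bronchodilator FEV1/FVC below 0.7. If no post test could be completed, a pre-bronchodilator ratio below 0.65 counts instead.
- **Clinically significant COPD**: the SAP reads "Participants with abnormal spirometry, defined as spirometrically defined COPD plus at least one of the following": FEV1 below 60% predicted, or at least one "exacerbation like event within the past 12 months". Protocol 1.1 and 4.1 use the same two severity criteria but require a post-bronchodilator ratio below 0.7 and give no fallback.
- **Mild COPD**: FEV1 of at least 60% and "No prior history of ECOPD". The SAP builds this on spirometrically defined COPD; the Protocol again requires the post-bronchodilator ratio.
- **PRISm**: not spirometric COPD, with post-bronchodilator FEV1 below 80% predicted. Only the SAP adds a rule for a missing post test. It begins "Among participants who do not complete post-bronchodilator spirometry and have pre-bronchodilator" FEV1/FVC of at least 0.7. Within that group, FEV1 of at least 80% means not PRISm, and FEV1 below 80% means undetermined.
- **Symptomatic non-obstructed (SNO)**: neither spirometric COPD nor PRISm, and CAT of at least 10.
- **No COPD**: listed as population 6 in SAP 9.3 and used in SAP 9.4 and 10.3, which point back to section 6.1 for it. Section 6.1 has no such row. Protocol 9.2 gives a rule for Aim 1 specificity only: FEV1/FVC of at least 0.70 on research spirometry.

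The baseline questionnaire records "History of respiratory symptoms and exacerbation like events over the past year" (SAP 7.6; the same in Protocol 8.1). In the tool's development study, the comparable mild group had "no ECOPD in the previous year" (Protocol 2.2).

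**The concern.** Two programmers working from these texts could build different cohorts. One rule, followed exactly, gives a definite non-obstructed label to people whose obstruction status was never established. Clinically significant and mild COPD look like the two halves of spirometric COPD, but as written they do not add up to it.

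These cohorts carry real analyses. Mild COPD is a secondary reference condition in Aim 1 (Protocol 1.1, 9.3.1) and a secondary population in Aim 3 (Protocol 3 and 9.3.2). SAP 11.2 repeats the primary comparison in populations 2 to 8, which include clinically significant COPD, mild COPD, No COPD and SNO.

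**Working it through.** No sample size, power figure or alpha depends on these definitions, so there is no stated figure to reproduce. The check applies the rules literally.

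**1. No post-bronchodilator test, CAT of at least 10 (SAP rules)**

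| Pre ratio | FEV1 % predicted | Spirometric COPD | PRISm | SNO |
|---|---|---|---|---|
| <0.65 | any | yes (fallback) | no | no |
| 0.65 to <0.70 | any | no | no rule applies | yes, as written |
| ≥0.70 | <80 | no | undetermined | not assigned |
| ≥0.70 | ≥80 | no | no | yes |

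The second and third rows are in the wrong order of certainty. A participant with a ratio of 0.75 and a low FEV1 is held as undetermined, while one with a ratio of 0.67 is labelled non-obstructed even at an FEV1 of 55% predicted.

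**2. Enumeration of profiles**

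Inputs: six pre/post ratio pairs (0.60/0.62, 0.60/none, 0.67/none, 0.67/0.66, 0.67/0.72, 0.75/none); FEV1 of 55, 65, 75 or 90% predicted; exacerbation history of never, only more than 12 months ago, or within 12 months; CAT of 12.

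- Pre ratio 0.67 with no post test: 1 × 4 × 3 = 12 profiles, and all 12 come out as SNO.
- Spirometric COPD under the SAP: three pairs qualify (0.60/0.62, 0.60/none, 0.67/0.66), so 3 × 4 × 3 = 36 profiles.
- Of those 36, in neither clinically significant nor mild COPD: FEV1 of 65, 75 or 90 with an older event only, so 3 × 3 × 1 = 9.
- With a 12-month window in both definitions: 0 of 36 in neither.
- In both clinically significant and mild COPD: 0 of 36 under either window.

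These are counts of profiles, not of patients.

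**3. Protocol against SAP**

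Take a pre ratio of 0.60, no post test and FEV1 of 55% predicted. Both documents call this spirometric COPD. The SAP then calls it clinically significant; the Protocol does not, because there is no post-bronchodilator ratio. Under the Protocol wording, all 1 × 4 × 3 = 12 profiles with pre ratio 0.60 and no post test are spirometric COPD but belong to neither severity group.

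**4. Is the look-back window usable?**

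Mild COPD has no stated window, and baseline history goes back one year. Read as a lifetime criterion, it cannot be derived from the data described. A 12-month window can be, and it matches the development study.

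**The case against.** The strongest reply is that little of this reaches the data. Only past-year events are recorded, so a participant whose last event was 18 months ago has no recorded event and would be programmed as mild; the two windows then coincide in practice. That stands, and it limits the third item to a wording defect. It does not remove it, because the programmer has to depart from the text to get there.

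The difference between Protocol and SAP may also be deliberate. The SAP covers Aim 3 and puts Aim 1 out of scope, and a strict post-bronchodilator reference standard suits a diagnostic accuracy aim. That is a fair reason to leave Aim 1 alone. It does not explain why the Protocol's cohort table, which also serves Aim 3, differs from the SAP's.

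The consequences are limited. The primary Aim 3 population is defined by CAPTURE result without spirometry. Protocol 9.1.2.2 calls the secondary practice-behaviour analyses exploratory. SAP 9.5 expects missing spirometry in only a small portion of patients and multiply imputes it in a sensitivity analysis, which may reclassify some participants but does not repair the main definitions. CAPTURE-negative participants in the band with pre-bronchodilator FEV1 of at least 70% predicted are followed only through the roughly 5% random sample.

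Four stronger readings are tempting and are not supported:

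- *Participants in the 0.65 to <0.70 band are obstructed.* Both documents determine obstruction after bronchodilator. The Amendment 2.0 rationale (Protocol 14) reports more than 95% agreement only for pre ratios below 0.65. Status in the band is unknown.
- *The band falls into No COPD.* The SAP does not define that population, and the Protocol 9.2 rule would exclude the band. The defect is a missing definition.
- *A participant with a past-year event could be in both severity groups, since nobody enrolled has diagnosed COPD.* Protocol 9.1.1.1 and 9.2 use ECOPD as the label for the same exacerbation-like event, so there is no overlap.
- *A sizeable share of mild patients belongs to no severity group.* Any such count needs records of older events, which the described data collection does not provide.

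**Conclusion.** The definitions need correcting, in order of weight: the SNO rule for the 0.65 to <0.70 band together with the undefined No COPD population; the Aim 3 mismatch between Protocol and SAP; and the missing window for mild COPD. The first two, followed as written, put participants in an unsupported cohort or in different cohorts. The third is a wording gap whose practical effect is probably small.

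The number of participants affected cannot be computed. The documents give no count of missing post tests by pre-bronchodilator ratio and no count of older exacerbations. The Amendment 2.0 rationale records several instances of failed or refused post-bronchodilator tests, so the situation does arise. SAP 13.1 reports roughly 2 spirometric COPD patients per practice, or about 2 × 100 = 200 over the planned 100 practices, so the COPD cohorts are small. Only secondary and exploratory cohorts are affected; the primary CAPTURE+ analysis is not.

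This rests on reading the SNO and mild COPD rules as written, and on the baseline questionnaire covering no more than the past year.

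**What to change.** In Protocol 1.1 and 4.1 and SAP 6.1:

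1. Class a pre-bronchodilator FEV1/FVC of 0.65 to <0.70 with no post test as undetermined for spirometric COPD, PRISm and SNO in primary analyses, extending the treatment that the SAP already gives PRISm.
2. Add a No COPD row to SAP 6.1 that requires a demonstrated FEV1/FVC of at least 0.70, consistent with Protocol 9.2.
3. Use one definition of clinically significant and mild COPD for Aim 3 in both documents. Building both on spirometrically defined COPD, as the SAP does, is the choice under which they can partition that cohort. Leave the Aim 1 reference standard in Protocol 9.2 as stated.
4. Replace the open-ended exacerbation criterion for mild COPD with no exacerbation-like event in the past 12 months, so that it complements the clinically significant definition.

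The cost is definition text and derived-variable code, with no new data. The one downside is that a few participants leave SNO, and any No COPD group built simply as not spirometric COPD, to become undetermined; report their number by arm.

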7.1 Inclusion Criteria

- Men or women between the ages of 45 and 80 years of age
- Ability to read and complete visit in English or Spanish
- Stated willingness to comply with all study procedures and availability for the one-year duration of the study
- Provision of signed and dated informed consent form

7.2 Exclusion Criteria

- Previous clinician diagnosis of COPD
- Treated respiratory illness (with antibiotics and/or systemic steroids) in the past 30 days prior to study visit
- Unable to perform spirometry due to any of the following conditions within the past 30 days of baseline
 - Chest surgery
 - Abdominal surgery
 - Eye surgery
 - Heart attack
 - Stroke
- Unwilling or unable to complete all components of the single study visit

7.3 Randomization and Blinding

Randomization: Practices will be randomized into one of the two interventions, COPD education or COPD education + CAPTURE education, in a 1:1 manner, stratified by PBRN. Randomization will occur at the time of site activation and each site will be assigned a unique randomization number. The DCC will prepare the randomization schedule, using computer-generated block randomization with the block size(s) known only by the DCC. A secure web-based application will be built that will be used by the central study coordinators to enter site information (e.g., site ID, stratification factor) and to obtain the randomization number. The information can be printed and sent and/or emailed directly to the study coordinator.

Blinding: This is a single-blind study with the participants blinded to whether their practitioners have received CAPTURE education and patient-level CAPTURE results. Practitioners at sites that are randomized to the control arm (COPD education alone) will be blinded to the CAPTURE questionnaire and PEF results. All practitioners and participants will be blinded to the baseline COPD status of the participants (i.e., blinded to spirometry results), except for safety reasons. In this situation, participants and their clinician will be notified if a participant's post-bronchodilator FEV₁ is less than 30% predicted. For all other

participants, they and their practitioners will be blinded to research spirometry results. The coordinator should make every effort to conceal the spirometry results from the participants in these latter cases. Study coordinators should also make every effort to conceal the administration of a post- bronchodilator spirometry test from the practice staff so as not to unblind the physicians to abnormal spirometry.

